7.7 Study Treatment: Vorinostat

Chemical Name: N-hydroxy-N'-phenyl-octane-1,8-dioic acid diamide; N-hydroxyl-N'-phenyl (9CI) octanediamide; suberoylanilide hydroxamic acid

Other Names: SAHA, L-001079038, WIN 64652, MSK390, AP390

Classification: Antineoplastic

CAS Registry Number: 149647-78-9

Molecular Formula: C₁₄H₂₀N₂O₃ **M.W.:** 264.32

Approximate Solubility: Water ≤ 5 mg/mL

Description: Histone deacetylase (HDAC) inhibitor

Mode of Action: Histone deacetylases (HDACs) are a family of enzymes that regulate chromatin remodeling and gene transcription via the dynamic process of acetylation and deacetylation of core histones.

Vorinostat, a potent inhibitor of HDAC activity, binds directly to the catalytic pocket of HDAC enzymes. It causes G1 or G2 phase cell-cycle arrest, apoptosis, or differentiation in cultured transformed cells.

How Supplied: Vorinostat is supplied free of charge by Merck and Co., Inc. Vorinostat is supplied as a white, opaque gelatin, size 3 capsule, containing 100 mg of vorinostat.

The inactive ingredients contained in each capsule are microcrystalline cellulose, sodium croscarmellose, and magnesium stearate.

Vorinostat 100 mg capsules are supplied in bottles containing 120 capsules.

Storage: Store vorinostat capsules at 20-25°C. Excursions permitted between 15 and 30 °C (59 to 86 °F).

Stability: Shelf life stability studies of the intact bottles are on-going.

Route of Administration: Orally

Method of Administration: Unless otherwise stated in the protocol, vorinostat capsules must be administered whole. It is recommended that vorinostat be taken with food.

Patients should not make up missed doses. If a patient has an episode of emesis after taking vorinostat, patient should be instructed not to take an additional dose.

Potential Drug Interactions: The major pathways of vorinostat metabolism involve glucuronidation and β -oxidation. As vorinostat is not eliminated via CYP450 pathways, no drug-drug interactions are expected with known CYP450 inhibitors or inducers. Although vorinostat was not a potent reversible CYP450 inhibitor, studies performed to monitor gene expression changes indicated some potential for CYP2C9 and CYP3A4 activity suppression. However, these changes were observed at concentrations higher than the pharmacologically relevant concentration of 2 μ M (Cmax).

Prothrombin time and INR prolongations have been reported in patients taking vorinostat concomitantly with coumarin derivative anticoagulants. Monitor these patients more frequently for alterations in their coagulation parameters.

Special Handling: Vorinostat is an anticancer drug. Clean powder spills from broken or damaged vorinostat capsules carefully minimizing inhalation. Wash spill area at least 3 times with ethyl alcohol, followed by water.

Patient Care Implications: Because vorinostat's dose limiting toxicities are anorexia, dehydration, diarrhea, and fatigue, patients should maintain adequate fluid and food intake. Encourage patients to seek a nutritional consult. Patients should be instructed to drink at least 2 liters of fluids daily to prevent dehydration.

Treat diarrhea promptly with appropriate supportive care, including loperamide. Instruct patients to begin taking loperamide at the first signs of: 1) poorly formed or loose stool, 2) occurrence of more bowel movements than usual in one day, or 3) unusually high volume of stool. Loperamide should be taken in the following manner: 4 mg at first onset of diarrhea, then 2 mg after each unformed stool. Daily dose should not exceed 16 mg/day. Loperamide should not be taken

prophylactically. Advise patients to drink plenty of clear fluids to help prevent dehydration caused by diarrhea. Avoid loperamide if there is the presence of blood or mucus in the stool or if diarrhea is accompanied by fever. If grade 3 or 4 diarrhea develops, discontinue further treatment with vorinostat.

Patients should not have taken valproic acid, another histone deacetylase inhibitor, for at least 2 weeks prior to study enrollment.

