4.5.6 Expected Adverse Events

The types of adverse experiences observed in clinical trials of vorinostat were those usually associated with chemotherapy, such as nausea, fatigue, diarrhea, anorexia, vomiting, constipation and cytopenias. The three major clinical categories of adverse experiences attributable to vorinostat include a constellation of gastrointestinal symptoms, constitutional complaints, and cytopenias. However, most of the adverse experiences were manageable. In fact, most of the very common adverse experiences were reversible and could be managed using conventional supportive care for chemotherapy. On the whole, treatment with oral vorinostat was well tolerated for use in the outpatient setting. Please see below for specific information regarding vorinostat-related adverse experiences observed when vorinostat was administered either as monotherapy or in combination with other agents, in Merck-sponsored clinical trials.

Nausea and Vomiting

Drug-related nausea and vomiting are commonly observed with vorinostat therapy: 51.3% all grades nausea, 4.9% grades 3-5 nausea; 32.5% all grades vomiting, 3.2% grades 3-5 nausea. Nausea and vomiting should be managed according to standard practice as outlined in the published American Society of Clinical Oncology (ASCO) antiemetic guidelines. Briefly, antiemetic agents including, but not limited to, 5HT-3 antagonists, aprepitant, lorazepam, diphenhydramine or phenothiazines may be considered. The use of empiric anti-emetic coverage is strongly encouraged, as is early and aggressive management of nausea, decreased oral intake and/or vomiting in patients treated with vorinostat.

Diarrhea

Drug-related diarrhea is commonly with vorinostat therapy: 43.5% all grades diarrhea, 6.7% grades 3-5 diarrhea. Diarrhea should be treated promptly with appropriate supportive care. Patients should be instructed to begin taking loperamide at the first sign of: 1) poorly formed or loose stool, 2) occurrence of more bowel movements than usual in one day or 3) unusually high volume of stool. Diarrhea should be managed with loperamide or according to institutional guidelines. However, loperamide should be deferred if blood or mucus is present

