7.7.1 Vorinostat Dose/Delay Modification Guidelines

Note: If vorinostat is dose-reduced or held for toxicity, and the toxicity is most likely attributed to vorinostat and not attributed to pembrolizumab, administration of pembrolizumab can continue.

Vorinostat dose reductions are NOT permitted during the DLT period. Following the completion of the DLT period, the vorinostat doses may be modified for toxicity according to the below guidelines in Tables 6 and 7. Vorinostat dose delays are permitted during the DLT period due to study treatment-related toxicity, however, if a patient misses > 30% of the vorinostat doses due to toxicity, this will be considered a DLT.

Table 6. Vorinostat Dose Reduction Guidelines

Vorinostat Dose Reductions				
Starting dose	1 st dose reduction	2 nd dose reduction	3 rd dose reduction	4 th dose reduction
Dose Level 1	Dose Level -1	Dose Level -2	Dose Level -2 schedule but 100mg daily	N/A**
Dose Level 2	Dose Level 1	Dose Level -1	Dose Level -2	Dose Level -2 schedule but 100mg daily

mg = milligrams; po = orally; BID = twice daily

**Patients requiring a dose reduction to below 100 mg daily of vorinostat at dose level -2 schedule will discontinue vorinostat permanently.

Table 7. Vorinostat Dose Delay Guidelines

Grade of Event	Management/Next Dose for Vorinostat
≤ Grade 1	No change in dose.

Grade 2	If tolerable to patient, no change needed but monitor patient more frequently. If intolerable to patient, hold* drug until toxicity \leq Grade 1 then resume drug at same dose.
Grade 3 (1 st occurrence)	Hold* until \leq Grade 1. Resume at same dose.
Grade 3 (after 1 st dose reduction)	Hold* until \leq Grade 1: if toxicity related to drug, resume at 1 dose lower; if toxicity not related to drug, resume at same dose or 1 dose lower.**
Grade 3 (subsequent occurrences)	Hold* until \leq Grade 1: if toxicity related to drug, resume at 1 dose lower; if toxicity not related to drug, resume at same dose or 1 dose lower**.
Grade 4	Discontinue vorinostat. However, if patient is clearly benefiting from treatment, may continue after recovery to \leq Grade 1 at PI's discretion.

*If optimally managed, patients requiring a delay of >2 consecutive weeks will discontinue vorinostat

**Patients requiring a dose reduction to below 100 mg daily of vorinostat at dose level -2 schedule will discontinue vorinostat permanently.

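### Section 7.7 stops vorinostat for Grade 3 or 4 diarrhoea while Table 7 lets it resume, with no stated precedence; the clash is mainly for Grade 3 events after cycle 2

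*Combined protocol and SAP*

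**What the plan says.** The patient-care text of Section 7.7 reads: "If grade 3 or 4 diarrhea develops, discontinue further treatment with vorinostat". It carries no condition.

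Section 7.7.1 opens its modification rules by saying that, once the DLT period is over, "the vorinostat doses may be modified for toxicity according to the below guidelines in Tables 6 and 7". Table 7 then works by grade, for any toxicity:

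- Grade 3, first occurrence: hold until "Grade 1. Resume at same dose".
- Grade 3 after a first dose reduction, and subsequent Grade 3 occurrences: hold, then "if toxicity related to drug, resume at 1 dose lower"; if unrelated, resume at the same dose or one lower.
- Grade 4: "Discontinue vorinostat. However, if patient is clearly benefiting from treatment, may continue after recovery to" Grade 1 or less, at the PI's discretion.

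A footnote turns a long hold into a stop: "patients requiring a delay of >2 consecutive weeks will discontinue vorinostat".

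Table 5 (Section 7.6.1.2) covers pembrolizumab. It withholds that drug for Grade 2 or 3 diarrhoea/colitis and stops it permanently for Grade 4. The text before the table says that when Table 5 leads to a permanent stop of pembrolizumab, vorinostat is to go on.

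**The concern.** Diarrhoea is the last toxicity on which this protocol should be ambiguous. Section 7.7 names it among vorinostat's dose-limiting toxicities, and Section 4.4.6 lists it as expected with pembrolizumab in at least 10% of patients. A clinician with a Grade 3 case after cycle 2 finds an unconditional stop in one section and a hold-and-resume rule in the next.

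The first issue is patient safety, because the instructions decide whether the patient is exposed again. The second is the data. Toxicity is the primary endpoint, and determining the RP2D is a primary objective. Section 7.3 lets the principal investigator choose an RP2D below the MTD partly on the strength of dose reductions in later cycles. The same event could leave a record of permanent discontinuation, same-dose resumption or dose reduction, depending on which text was followed.

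**Working it through.** The plan gives no figure to reproduce. The check is a comparison of the texts, followed by one scale calculation.

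**Step 1. The instructions for vorinostat, side by side.**

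| Event | Section 7.7 | Table 7 (after the DLT period) | Section 7.6.1.2 with Table 5 |
|---|---|---|---|
| Grade 3 diarrhoea, first | Discontinue | Hold, resume at same dose | No permanent stop of pembrolizumab, so no vorinostat instruction |
| Grade 3 diarrhoea, later | Discontinue | Hold, resume one level lower if related; same or one lower if not | As above |
| Grade 4 diarrhoea | Discontinue | Discontinue, with a PI exception after recovery | If pembrolizumab is permanently stopped, vorinostat goes on |

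**Step 2. Is there a bridging sentence?** Section 7.7 does not mention Table 7. Section 7.7.1 and Table 7 contain no diarrhoea exception. The action column of Table 5 directs pembrolizumab only. No order of precedence is given.

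**Step 3. When does the clash arise?** The DLT period is 42 days (2 cycles x 21 days), and Tables 6 and 7 are introduced for the time after it. Within it, a clinically relevant Grade 3 event judged at least possibly treatment-related is a DLT. The exceptions in Section 7.2 name nausea, fatigue and vomiting, but not diarrhoea. Section 7.12 lists a DLT among the reasons a subject must be discontinued. For such events in cycles 1 and 2, Sections 7.7 and 7.12 therefore point the same way. From cycle 3, with treatment allowed for up to 24 months, Table 7 applies and the Grade 3 rows conflict with Section 7.7.

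**Step 4. Grade 4.** Section 7.7 and the Table 7 default agree; they part only on the PI exception. Section 7.12, through the unacceptable-toxicity definition in Section 10.2, also appears to call for discontinuation after a related Grade 4 event at any time on therapy. Section 7.6.1.2 points the other way when pembrolizumab has been permanently stopped under Table 5.

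**Step 5. Scale, as an assumption only.** Section 4.5.6 reports "43.5% all grades diarrhea, 6.7% grades 3-5 diarrhea" as drug-related rates in other vorinostat trials, alone or in combination. If 6.7% applied here:

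- expected sample size: 0.067 x 52 = 3.5 patients
- maximum accrual: 0.067 x 60 = 4.0 patients

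These counts cover all cycles. They include events in cycles 1 and 2, which mostly fall outside the conflict.

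**The case against.** The best defence is that the specific rule governs the general one: Section 7.7 speaks of diarrhoea, while Table 7 speaks only of grades. That is a natural reading, but it remains an inference. A clinician could as reasonably hold that the section titled as the dose and delay guideline overrides a patient-care paragraph.

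A second defence is that discontinuing need not be final. Table 7's Grade 4 row uses the word and then allows continuation, whereas final stops elsewhere are described as permanent. This has some weight. It does not remove the conflict: Table 7 treats holding and discontinuing as separate actions, its footnote converts one into the other only after more than two consecutive weeks, and Section 7.7 gives no condition for restarting.

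The objections on scope and size stand. A reader might infer that the contradiction runs through all cycles and both grades equally; Steps 3 and 4 show that it does not. A reader might also take 6.7% as this regimen's rate. Section 4.5.5 says tolerability depends on total daily dose and consecutive dosing days, with 200 to 900 mg daily studied. Dose Levels 1 and 2 here give 200 or 400 mg daily on 10 of 21 days. The same section places most single-agent vorinostat DLTs in the first month. The documents do not quantify any added immune-related colitis under the combination.

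It is also fair that discontinuation and dose-reduction rates are not planned summaries, that the DLT and unacceptable-toxicity rules count adverse events rather than stops, and that the trial summary lists one participating site. The likely variation is between clinicians, not sites.

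**Conclusion.** The contradiction is real and rests on the text alone. It is firmest for Grade 3 diarrhoea after cycle 2, where Section 7.7 stops vorinostat and Table 7 resumes it. For Grade 4 it is narrower, limited to the PI exception and to the instruction in Section 7.6.1.2 to carry on with vorinostat. It bears on patient safety, on vorinostat exposure and on the dose-reduction information that may inform the RP2D.

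The size is small and uncertain: about 3.5 of 52 patients (4.0 of 60) over all cycles if the rate from other trials carried over, and probably fewer in the window where the rules conflict. A reader might go further and conclude that the DLT evaluation or the toxicity stopping rule is compromised. The documents do not support that, because neither depends on how vorinostat is handled after an event has been counted.

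**What to change.** Reconcile Section 7.7 with Table 7, and both with Section 7.6.1.2 and the diarrhoea/colitis row of Table 5, so that the protocol gives one vorinostat instruction for Grade 3 diarrhoea and one for Grade 4. State which text governs, and whether the instruction depends on occurrence, attribution or the DLT period. Check the result against the discontinuation list in Section 7.12. Which clinical rule to adopt is the sponsor's decision.

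The cost is a short protocol clarification; the design, sample size and analysis do not change.

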7.7.1 Vorinostat Dose/Delay Modification Guidelines

Note: If vorinostat is dose-reduced or held for toxicity, and the toxicity is most likely attributed to vorinostat and not attributed to pembrolizumab, administration of pembrolizumab can continue.

Vorinostat dose reductions are NOT permitted during the DLT period. Following the completion of the DLT period, the vorinostat doses may be modified for toxicity according to the below guidelines in Tables 6 and 7. Vorinostat dose delays are permitted during the DLT period due to study treatment-related toxicity, however, if a patient misses > 30% of the vorinostat doses due to toxicity, this will be considered a DLT.

Table 6. Vorinostat Dose Reduction Guidelines

Vorinostat Dose Reductions				
Starting dose	1 st dose reduction	2 nd dose reduction	3 rd dose reduction	4 th dose reduction
Dose Level 1	Dose Level -1	Dose Level -2	Dose Level -2 schedule but 100mg daily	N/A**
Dose Level 2	Dose Level 1	Dose Level -1	Dose Level -2	Dose Level -2 schedule but 100mg daily

mg = milligrams; po = orally; BID = twice daily

**Patients requiring a dose reduction to below 100 mg daily of vorinostat at dose level -2 schedule will discontinue vorinostat permanently.

Table 7. Vorinostat Dose Delay Guidelines

Grade of Event	Management/Next Dose for Vorinostat
≤ Grade 1	No change in dose.

Grade 2	If tolerable to patient, no change needed but monitor patient more frequently. If intolerable to patient, hold* drug until toxicity \leq Grade 1 then resume drug at same dose.
Grade 3 (1 st occurrence)	Hold* until \leq Grade 1. Resume at same dose.
Grade 3 (after 1 st dose reduction)	Hold* until \leq Grade 1: if toxicity related to drug, resume at 1 dose lower; if toxicity not related to drug, resume at same dose or 1 dose lower.**
Grade 3 (subsequent occurrences)	Hold* until \leq Grade 1: if toxicity related to drug, resume at 1 dose lower; if toxicity not related to drug, resume at same dose or 1 dose lower**.
Grade 4	Discontinue vorinostat. However, if patient is clearly benefiting from treatment, may continue after recovery to \leq Grade 1 at PI's discretion.

*If optimally managed, patients requiring a delay of >2 consecutive weeks will discontinue vorinostat

**Patients requiring a dose reduction to below 100 mg daily of vorinostat at dose level -2 schedule will discontinue vorinostat permanently.

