7.1 Treatment Allocation

There will be no randomization or stratification as part of this study. All patients who consent to the study, meet eligibility criteria, and are registered on the trial will receive study treatment.

This is a phase I study, including a dose-escalation portion of the study with 2 dose levels and 2 possible de-escalation dose levels, for a total of 4 possible dose levels. The starting dose will

be 100mg of vorinostat twice a day (BID), and 200mg IV pembrolizumab. Subjects will receive oral vorinostat according to dose level schedule and dose. Pembrolizumab will be administered on day 1 of each cycle thereafter. Study therapy will be administered in 21-day cycles. The planned dose levels in the dose-escalation portion of the study are outlined in Table 3 below.

Once the RP2D has been determined, an expansion cohort of 40 patients will be enrolled and treated at the RP2D, to acquire additional safety and tolerability data about the combination.

Table 3. Phase I Dose Levels

Dose Level	Vorinostat	Pembrolizumab (day 1)
-2	100mg PO BID, d1-3, 8-10	200mg IV
-1	100mg PO BID, d1-3, 8-10, 15-17	200mg IV
1 (starting)	100mg PO BID, d1-5, 8-12	200mg IV
2	200mg PO BID, d1-5, 8-12	200mg IV

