7.1.1 Treatment Duration

Study treatment will continue until the subject completes 24 months of treatment with the study regimen, or experiences radiographically-confirmed PD (Section 9.2.6 and Section 9.2.6.1), unacceptable adverse experiences, either DLT (Section 7.2) or other unacceptable toxicity (section 10.2), or meets other criteria for study withdrawal or treatment discontinuation

7.1.2 Rules for Phase I Dose Escalation, De-Escalation and Expansion: Adapted Rolling 6 Design

This phase I trial will employ a modified Rolling 6 design, a more conservative version of the Rolling 6 design of Skolnik, et al²⁹. In this design, at most, 3 patients will be under observation for DLT on the current test dose level at any time. Patients who are not evaluable for DLT will be replaced. Once each patient is evaluable for toxicity and passes without a DLT, an additional patient *may* be accrued on that dose level – up to 6 patients. Once 3 patients are evaluable with no patient at that dose level experiencing a DLT, the dose can be escalated, or up to 3 additional patients may be treated at the current dose level. Although this design does not require that 6 patients be treated, no more than 6 evaluable patients will be accrued to any dose level during the dose finding portion of this study. If at any time, the dose level has 1 documented DLT with fewer than 6 evaluable patients, accrual will continue until 6 patients are evaluable. Escalation will terminate as soon as two or more patients experience any DLT attributable to the study treatment, at a given dose level. MTD will be declared at the highest dose level at which 6 patients have been treated and at most 1/6 patients experiences DLT. If more than 1/6 patients experiences DLT, then the next lower dose will be expanded. There will be no intrapatient dose escalation. These rules are outlined in Table 4:

Table 4. Dose Escalation Rules

# Patients on Current Level			Action
With DLT [^]	Evaluable	Evaluable + At Risk [^]	
0	0	1-2	Accrue next patient at this level*
0	0	3	Hold accrual
0	1	1-3	Accrue next patient at this level
0	1	4	Hold accrual
0	2	2-4	Accrue next patient at this level
0	2	5	Hold accrual
0	3-6	3-6	Accrue next patient at the next higher level* ^{+,+}
1	1	1-2	Accrue next patient at this level
1	1	3	Hold Accrual
1	2	2	Accrue next patient at this level
1	2	3-4	Hold accrual
1	3-5	3-5	Accrue next patient at this level
1	3-5	6	Hold accrual
1	6	6	Accrue next patient at the next higher level*

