7.2 Definition of Dose-Limiting Toxicity

The dose-limiting toxicity (DLT) observation period will be 42 days (2 cycles). DLT assessment will occur on cycle 3, day 1 prior to receipt of cycle 3, day 1 of study therapy. Toxicities will be graded according to the National Cancer Institute Common Terminology Criteria for Adverse Events (CTCAE, Version 4.03) accessible at:

http://evs.nci.nih.gov/ftp1/CTCAE/CTCAE_4.03_2010-06-14_QuickReference_5x7.pdf

DLT will be defined as one of the following AEs that is at least possibly related to study treatment.

Hematologic

- Grade 4 neutropenia lasting > 7 days (despite the use of growth factor support).
- Grade 4 thrombocytopenia lasting > 7 days or requiring platelet transfusion.
- Grade 3 or 4 thrombocytopenia associated with grade 2 or higher bleeding.
- Grade 4 anemia not associated with lymphoma.

- Any Grade 5 AE.

Non-hematologic

- Grade ≥ 3 pneumonitis that does not resolve to grade ≤ 1 within 3 days after initiation of supportive care measures.
- Any clinically relevant grade 3 or grade 4 AE with the exception of:
 - Grade 3 asymptomatic laboratory abnormalities, including lipase or amylase, that are not clinically relevant, not requiring hospitalization or delay of treatment.
 - Grade 4 laboratory abnormalities including, but not limited to, hypo- or hyperglycemia, hypo- or hypernatremia, hypo- or hyperkalemia, hypo- or hypermagnesemia, hypo- or hyperphosphatemia, or hyperuricemia that resolve within 48 hours to Grade ≤ 2 with supportive measures.
 - Grade 3 nausea, or fatigue controlled with supportive measures.
 - Grade 3 vomiting if the subject does not require total parenteral nutrition (TPN), tube feeding, or hospitalization, and the toxicity improves to $<$ grade 3 within 72 hours.
 - Grade 3 asymptomatic endocrinopathy.
 - Grade 3 fatigue related to endocrinopathy that resolves within 7 days of hormone-replacement or corticosteroid therapy.
 - Grade 3 local inflammatory response attributed to local antitumor response.
 - Vitiligo or alopecia of any grade.
- Any Grade 5 AE.

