7.4 Replacement of Subjects

During the Phase I dose escalation portion of the study, subjects will be replaced for any of the following:

- Missed 30% or more doses of vorinostat during the DLT period (not due to DLT).
- Did not receive the dose of pembrolizumab during the DLT period.
- Study drug discontinuation for any reason other than DLT during the DLT period.

Subjects who are replaced for missed doses may continue to receive study treatment if there is clear clinical benefit, but will not be included in DLT analysis.

During the expansion cohort portion of the study, subjects who discontinue study therapy prior to the first tumor response assessment for a reason other than progressive disease will be replaced.

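### Sections 7.4 and 7.7.1 draw the 30% missed-dose line with different inequalities, so a patient missing exactly 12 of 40 vorinostat doses for toxicity is replaced rather than classified as DLT or non-DLT

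*Combined protocol and SAP*

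**What the plan says.** Two sections of the combined protocol and SAP set a 30% threshold for missed vorinostat doses during the DLT period.

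- **Section 7.4 (Replacement of Subjects)** lists among the reasons for replacement in dose escalation: "Missed 30% or more doses of vorinostat during the DLT period (not due to DLT". Subjects replaced for missed doses may stay on treatment if they benefit, "but will not be included in DLT analysis".
- **Section 7.7.1 (Vorinostat Dose/Delay Modification Guidelines)** bars dose reductions in the DLT period but allows delays for treatment-related toxicity. It adds that "if a patient misses > 30% of the vorinostat doses due to toxicity, this will be considered a DLT".

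Section 7.1.2 repeats the general principle: "Patients who are not evaluable for DLT will be replaced". Section 7.2 sets the window: "The dose-limiting toxicity (DLT) observation period will be 42 days (2 cycles". Neither the DLT list in 7.2 nor Table 4 mentions missed doses, so 7.7.1 is the only place where they become a DLT.

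**The concern.** The two rules should divide patients cleanly. Doses missed because of toxicity bear on tolerability, whereas doses missed for other reasons may leave a patient uninformative about it. With one rule starting at 30% and the other only above it, a patient exactly on the line for a toxicity that 7.2 does not list has not met the 7.7.1 DLT criterion. The miss is therefore not due to a DLT, the exemption in 7.4 does not apply, and the patient is replaced.

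Determining the MTD is a primary objective, and one patient can decide it. At most 1 DLT in 6 allows a level to be declared the MTD, while 2 DLTs close it. If a level already has one DLT, the outcome may turn on whether this patient is a DLT, a non-DLT or absent from the count.

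**Working it through.** The plan states no figure to reproduce here. The check is whether exactly 30% can occur, and which rule then applies.

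**Inputs**
- Schedules (Section 7.1, Table 3): level 1 is "100mg PO BID, d1-5, 8-12" and level 2 is "200mg PO BID, d1-5, 8-12", each 10 dosing days per 21-day cycle. Level -1 has 9 dosing days per cycle and level -2 has 6. All are twice daily.
- DLT period (Section 7.2): 2 cycles.
- Assumption: the denominator in 7.7.1 is the doses scheduled in the DLT period, the period that 7.4 names.

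**Step 1: doses scheduled in the DLT period** = dosing days per cycle × 2 doses × 2 cycles.

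| Level | Scheduled doses | 30% of doses | 7.4 applies from | 7.7.1 applies from |
|---|---|---|---|---|
| 2 | 10 × 2 × 2 = 40 | 12.0 | 12 | 13 |
| 1 | 10 × 2 × 2 = 40 | 12.0 | 12 | 13 |
| -1 | 9 × 2 × 2 = 36 | 10.8 | 11 | 11 |
| -2 | 6 × 2 × 2 = 24 | 7.2 | 8 | 8 |

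The rules separate only where 30% is a whole number of doses, at levels 1 and 2. Twelve doses are 6 of 20 dosing days, for example a three-day hold in each cycle (3 × 2 × 2 = 12). Section 7.7 says missed doses are not made up, so held doses stay missed.

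**Step 2: classification at levels 1 and 2, doses missed for a toxicity that is not a DLT under 7.2**
- 11 of 40 (27.5%): neither rule applies; evaluable without DLT.
- 12 of 40 (30.0%): 7.4 applies and 7.7.1 does not; replaced and outside the DLT analysis.
- 13 of 40 (32.5%): 7.7.1 applies and 7.4 exempts the miss; DLT.

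**Step 3: possible effect on the MTD rule (illustration only).** Let p be the true DLT rate if boundary patients count as DLTs, and q the share of all patients exactly on the boundary. The documents give neither; p = 33% and q = 2 to 5 percentage points are assumptions. The chance that a level passes is P(at most 1 DLT in 6) = (1 − r)^6 + 6r(1 − r)^5, where r is the rate the trial would count:
- boundary patients counted as DLT, r = p = 0.33: 0.358;
- replaced, r = (p − q)/(1 − q) = 0.316 to 0.295: 0.386 to 0.432;
- counted as non-DLT, r = p − q = 0.31 to 0.28: 0.399 to 0.464.

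The present text falls between the two harmonised versions. With p = 25%, replacement moves the probability from 0.534 to 0.571–0.630; with p = 40%, from 0.233 to 0.253–0.286.

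**The case against.** **Escalation appears to be over.** Section 4.6.4 reports 42 patients enrolled and adds 10 with Hodgkin lymphoma to the expansion cohort. 42 + 10 = 52, the planned total of 12 + 40 in Section 11.3. Expansion opens only after the RP2D is set (Section 7.5), and the missed-dose replacement rule covers escalation only. This stands: changing the text now would probably alter no future MTD decision. What remains is how past escalation patients were classified and how that is reported.

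**A reader might infer that the mismatch can only hide toxicity.** The documents do not support that. It presumes that 30% missed for toxicity was meant to be a DLT. If the sponsor meant more than 30% in both places, the patient would be an evaluable non-DLT, and replacement is then the more cautious outcome, as Step 3 shows.

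**A reader might also infer that the patient's toxicity is lost.** It is not. All-grade toxicities in cycles 1 and 2 are recorded (Section 9.2.2) and summarised (Section 11.1.2), and the principal investigator may choose a lower RP2D on toxicity grounds (Section 7.3). The patient leaves the formal DLT count, not the safety data.

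**The affected group is narrow.** Most clinically relevant Grade 3–4 non-haematologic events are already DLTs under 7.2. That leaves mainly intolerable Grade 2 events, the excepted Grade 3 events and cytopenias short of DLT, with exactly 12 doses missed. This stands, and it limits the weight of the point. It does not resolve the conflict, because no other section settles the boundary.

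**Conclusion.** The inconsistency is real and minor. As written, 7.4 and 7.7.1 send one attainable missed-dose count, 12 of 40 at dose levels 1 and 2, to replacement, while the counts on either side are classified as non-DLT and DLT. Levels -1 and -2 have no such gap.

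This rests on reading the 7.7.1 denominator as the doses scheduled over 42 days, and on the toxicity not already being a DLT under 7.2. The direction of any effect on the DLT count depends on which boundary the sponsor adopts, and the documents do not say which was intended. They also give no frequency, so the probabilities above show only what could follow under stated assumptions. Nothing in the documents shows that any patient fell on the boundary or that the MTD or RP2D was wrongly determined.

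**What to change.** 1. Reconcile Sections 7.4, 7.7.1 and 7.2 on one boundary of the sponsor's choosing. With 30% or more in both rules, 12 of 40 missed for toxicity is a DLT; with more than 30% in both, it triggers neither rule and the patient is evaluable without a DLT on this criterion.
2. State the order: doses missed for treatment-related toxicity are classified under 7.7.1 first, and the missed-dose criterion in 7.4 then covers only doses missed for other reasons. No patient is then replaced for toxicity-related missed doses.
3. State the 7.7.1 denominator, and refer to the missed-dose criterion in 7.2.
4. As escalation appears complete, use the vorinostat diaries (Section 9.1.7) to check whether any replaced escalation patient missed exactly 12 of 40 doses for toxicity, and report the result, including if there was none.

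The cost is one symbol, a sentence or two and a short record check. Depending on the boundary chosen, an occasional patient who would now be replaced would count as a DLT or as an evaluable non-DLT.
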